13.6.3. Efficacy

SLE Flares and Severe Flares, and Renal Flares

Baseline Flares

• Baseline flares will be summarized using the data from the eCRF SFI data collection for the Day 0 visit. Per eCRF completion guidelines, the data collected at the Day 0 visit represents the flare data since the previous visit (i.e. the last visit in the feeder continuation study).

SLE Flares and Severe SLE Flares

2018N381035_00 BEL116027

SLE Flares and Severe Flares, and Renal Flares
CCI - This section contained Clinical Outcome Assessment data collection questionnaires or indices, which are protected by third party copyright laws and therefore have been excluded.

- SFI reports the first mild /moderate or severe flare occurrence since the last visit assessment.
- The SLEDAI criteria will be assessed programmatically to determine if the SELENA SLEDAI criteria for a flare has been met and used for the assessment of flare, irrespective of what was recorded on the SFI form.
- Although there are boxes on the form for the investigator to classify the most recent flare to mild/moderate or severe, the classification will be re-derived from the subcategory scores. Flares originally marked severe will be downgraded to "Not Severe" if the only reason marked is a change in SELENA SLEDAI score to > 12.
- In this case, if any of the mild/moderate reasons are checked or if the modified SELENA SLEDAI score has a change from previous visit of at least 3, then the flare will be considered Mild/Moderate.
- Flares that are marked mild/moderate where the only reason checked is SELENA SLEDAI increase of at least 3 points but not more than 12 points will be re-derived using the modified SELENA SLEDAI score.
- If it's found that the change is not actually ≥ 3 , and no other reasons are checked,

SLE Flares and Severe Flares, and Renal Flares

then the flare will not be counted.

Renal Flares

A SLE Renal flare is defined as the occurrence of at least 1 or more of the following in 2 or more consecutive visits during the study. (NB: at least 1 of the same criteria must be present on at least 2 consecutive visits)

Increased Proteinuria (using spot urine)

A reproducible increase in 24-hour urine protein levels (as measured in uPCR) to:

```
• >1g if the baseline (Day 0)value was <0.2g
```

OR

• >2g if the baseline (Day 0) value was between 0.2g and 1g

OR

• More than twice the value at baseline (Day 0) if the baseline value (Day 0)was >1g

Impaired Renal Function

- A reproducible decrease in GFR of >20%, accompanied by proteinuria (>1), and/or cellular (RBC and WBC) casts.
- [Alarcón-Segovia, 2003].

GFR is estimated by the Cockcroft-Gault equation [Cockcroft, 1976] for creatinine clearance in mL/min.

Cockcroft-Gault Equation

$$Cl_{cr} (mL/min) = \frac{(140\text{-}age (yrs)) \text{ x weight (kg)}}{72 \text{ x serum creatinine (mg/dL)}} \text{ x } 0.85 \text{ if female}$$

"Reproducible" requires the criterion to be met at two consecutive visits, including unscheduled visits.

The following table identifies the lab parameters to be used to evaluate the criteria in the renal flare definition above.

Criterion	Parameter	SI Dataset LBTESTCD
Proteinuria	Urine Protein:Creatinine Ratio (mg/mg)	PRTCRT_URQ
GFR	Creatinine Clearance estimated by the Cockcroft-Gault equation (mL/min)	CRTCE_PLR
Cellular casts:		
WBC cellular casts	WBC cellular casts	WBCSTM_URQ
dysmorphic RBCs	dysmorphic RBCs	DRBCM_URQ

SLE Flares and Severe Flares, and Renal Flares

Derivation for rates of SFI flares

• Within a treatment group, the unadjusted flare (severe flare) rate per subject-year in a given phase will be calculated as:

Unadjusted flare (severe flare) rate per subject-year =

total number of flares (severe flares) in the phase / total number of years of follow-up time in the phase.

• The calculation will not include baseline flares in the 116027 study.

Follow-up time derivation for rates of SFI flares		
Phase	Treatment Group	Definition
52-week Treatment Phase	TC, LTD	(Week 52/Exit visit date – Day 0 date + 1)/ 365.25 .
TH Phase	TH	(Week 24/TX re-start date – Day 0 date + 1)/ 365.25 .
RS Phase	TH	(Week 52/Exit visit – Week 24/TX re-start date)/ 365.25.

SELENA SLEDAI Organ System Domains

SELENA SLEDAI assessments consist of 24 individual weighted items in which signs and symptoms, laboratory tests, and physician's assessment for each of 8 organ systems are given a weighted score and summed if present (marked 'Yes') at the time of the visit or in the preceding 10 days. The maximum theoretical score is 105 (all 24 descriptors present simultaneously) with 0 indicating inactive disease (marked 'No'), but in practice few subjects have scores > 45 [Buyon, 2005; Petri, 2005].

Organ system domain scores are the sum of the weights of items within the organ domain as defined in the table below.

In this study, proteinuria is evaluated using spot-urine protein [represented as protein-creatinine ratio or PC Ratio (Add ref to 9.3.13) in the laboratory dataset] in lieu of the 24-hour urine collection. PC ratio in mg/mg is considered equivalent to g/24-hr urine protein.

If the P/C ratio value is missing, then the value from the previous visit will be used. Specifically, the assessment for proteinuria indicated on the CRF will be used to calculate the SELENA SLEDAI score. In the eCRF, laboratory items on the SLEDAI may also be ticked 'unknown' to indicate the lab test was not available. The laboratory items are: urinary casts, hematuria, proteinuria, pyuria, low complement, increased DNA binding, thrombocytopenia, and leukopenia. Responses of 'Unknown' will be managed via LOCF

List of organ systems, items, and weights for the assessments are provided.

Organ System	Descriptor	Weight	
[1] CNS	Seizure	8	
	Psychosis	8	
	Organic Brain Syndrome	8	
	Visual Disturbance	8	
	Cranial Nerve Disorder	8	
	Lupus Headache	8	
	CVA	8	
[2] Vascular	Vasculitis	8	
[3] Musculoskeletal	Arthritis	4	
	Myositis	4	
[4] Renal	Urinary Casts	4	
	Hematuria	4	
	Proteinuria	4	
	Pyuria	4	
[5] Mucocutaneous	Rash	2	
	Alopecia	2	
	Mucosal Ulcers	2	
[6] Cardiovascular & Respiratory	Pleurisy	2	
	Pericarditis	2	
[7] Immunologic	Low Complement	2	
	Increased DNA Binding	2	
[8] Constitutional	Fever	1	
[9] Hematologic	Thrombocytopenia	1	
-	Leukopenia	1	

PGA

- The PGA is collected on a 10cm visual analogue scale (VAS).
- The standard scoring range for the PGA is 0 to 3, and the score will be rescaled for standard reporting by multiplying the collected score by 3/10.
- During study conduct, it was noted that some sites erroneously received PGA scales that were 9.5cm in length due to a printing error, and some subjects utilized these scales before the error was discovered. Per Notes to File (08Jan2015, and 20Sep2017), an evaluation was performed and the decision was taken that this would result in minimal differences and not expected to affect any outcomes, and therefore it was unnecessary to adjust the analysis.

Prednisone Equivalent Conversion

Identification of Steroids

- A concomitant medication is identified as a steroid if
 - At least one associated ATC code (ATCCD1 ATCCD6) begins with 'H02.' AND
 - The route meets the following criteria:
 - Provides systemic exposure: oral, subcutaneous, intramuscular, intradermal, and intravenous.
 - Although not systemic, intra-articular steroids are also identified for

prohibited medication rules.

- Topical routes of administration are excluded (e.g., topical, conjunctival, intranasal).
- Steroid doses will be converted to the prednisone-equivalent dose.
- At data base release, all preferred terms identified with an ATC code beginning with 'H02' will be reviewed to ensure a conversion factor exists for all terms with a systemic or intra-articular route of administration.
- Similarly, all routes of administration for preferred terms with an ATC code beginning with 'H02' will be reviewed to ensure all systemic or intra-articular routes have been identified in the list above.
- In order to be converted, the frequency and dose of the steroid must be present with the unit dose in milligrams (mg).
- Reported dose for systemic steroid is converted to prednisone equivalent dose using conversion factor for each particular medication (refer to online calculator http://www.globalrph.com/corticocalc.htm).
 - Prednisone Equivalent Daily Dose (mg) = Collected Dose (mg) x Conversion Factor x Frequency Factor

Average Daily Dose Derivation

- Average daily prednisone dose at baseline is based on all days from the Screening visit date up to and including the Day 0 visit date.
- Post-baseline, average daily prednisone dose is based on all days between visits including the current visit date.
- Average Daily Dose (mg/day) = Sum of Prednisone Equivalent Daily Dose (mg) across all days in the visit interval / Number of days in the visit interval

Prednisone Conversion Factors (mg)	
	Conversion factor for converting to a
Preferred term	prednisone-equivalent dose
BETAMETHASONE	8.3333
BETAMETHASONE DIPROPIONATE	8.3333
BETAMETHASONE SODIUM PHOSPHATE	8.3333
BETROSPAM	8.3333
BUDESONIDE	0.3333
CELESTONA BIFAS	7.5
CORTISONE	0.2
CORTISONE ACETATE	0.2
CRONOLEVEL	8.3333
DEFLAZACORT	0.8333
DEPO-MEDROL MED LIDOKAIN	1.25
DEXAMETHASONE	6.6667
DEXAMETHASONE ACETATE	6.6667
DEXAMETHASONE SODIUM PHOSPHATE	6.6667
FLUOCORTOLONE	3
HYDROCORTISONE	0.25
HYDROCORTISONE ACETATE	0.25
HYDROCORTISONE SODIUM SUCCINATE	0.25
MEPREDNISONE	1.25
METHYLPREDNISOLONE	1.25
METHYLPREDNISOLONE ACETATE	1.25
METHYLPREDNISOLONE SODIUM	1.25
SUCCINATE	
PARAMETHASONE	2.5
PREDNISOLONE	1
PREDNISOLONE ACETATE	1
PREDNISOLONE SODIUM PHOSPHATE	1
PREDNISOLONE SODIUM SUCCINATE	1
PREDNISONE	1
PREDNISONE ACETATE	1
TRIAMCINOLONE	1.25
TRIAMCINOLONE ACETATE	1.25
TRIAMCINOLONE ACETONIDE	1.25
Frequency Factors	
Frequency	Factor
BID	2
BIW	2/7
OAM	1/30
Once	1
PRN	null
Q2H	12
Q2W	1/14
Q3H	8
QUII	

02M0	1/01
Q3MO	1/84
Q3w	1/21
Q4H	6
Q4W	1/28
Q6H	4
Q8H	3
QAM	1
QD	1
QH	24
QHS	1
QID	4
QOD	1/2
QPM	1
QW	1/7
QWK	1/7
TID	3
TIW	3/7
UNK	null
2 TIMES PER WEEK	2/7
3 TIMES PER WEEK	3/7
EVERY 2 WEEKS	1/14
EVERY 3 WEEKS	1/21
EVERY 4 Weeks	1/28
EVERY WEEK	1/7

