6.1.4. Definitions of SLE Flares Used in This Study

SLE flares are defined as:

• SFI Flare: A mild/moderate or severe flare according to the modified SELENA SLEDAI SLE Flare Index (modified excludes severe flares from the SELENA SLEDAI flare assessment that were triggered only by an increase in SELENA SLEDAI score to >12).

A SLE renal flare is defined as the occurrence of 1 or more of the following in 2 or more consecutive visits during the study:

- 1. A reproducible increase in 24-hour urine protein equivalent levels to
 - >1 g if the Day 0 value was <0.2 g,
 - >2 g if the Day 0 value was 0.2 to 1 g, or
 - More than twice the value at Day 0 if the Day 0 value is >1 g.
- A reproducible increase in GFR of >20% accompanied by at least one of the following: proteinuria (>1 g/24 hour equivalent), and/or cellular (RBC or WBC) casts [Alarcón-Segovia, 2003].

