11.5. Appendix 5: Clinical Laboratory Tests

Hematology	Urinalysis	Modified Chem-20
Total white blood cell count Differential: Absolute Neutrophils Band Neutrophils Myelocytes Metamylocytes Promyelocytes Lymphocytes Eosinophils Basophils Hemoglobin Hematocrit Red blood cell (RBC) count	Protein Glucose Ketones Occult blood Microscopic examination including: WBC per hpf RBC per hpf Dysmorphic RBC Casts (specified by type e.g., RBC, WBC) Spot Urine (protein : creatinine ratio) Urine Pregnancy	Electrolytes: Sodium Potassium Magnesium Chloride Carbon dioxide Calcium adjusted for Albumin Inorganic Phosphate Enzymes: SGOT (AST) SGPT (ALT) Alkaline Phosphatase Gamma glutanyl transpeptidase (GGT) Lactic dehydrogenase (LDH)
Platelet count Prothrombin time (PT) Partial thromboplastin time (PTT) Biological Markers BLyS protein Serum complement (C3 and C4) B-cell subtypes Immunoglobulins		Other: Creatinine Blood urea nitrogen (BUN) BUN/creatinine ratio Bilirubin, total Protein, total Albumin Uric acid Glucose Hepatitis B Viral DNA PCR Quantitative (HBV DNA) Estimated Creatinine Clearance/ GFR (Cockroft-Gault)
Serum immunoglobulin isotypes: IgG, I	gwi, igA	Liver event follow-up assessments: Hepatitis A IgM antibody HBsAg and hep B Core antibody (IgM) Hepatitis C RNA
Autoantibodies ANA Anti-dsDNA aCL		Hepatitis delta antibody Cytomegalovirus IgM antibody Epstein-Barr viral capsid antigen IgM antibody Hepatitis E IgM antibody CPK Anti-smooth muscle antibody Type 1 anti-liver kidney microsomal antibodies PK IgG Fractionated bilirubin Serum acetaminophen

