Subjects in the treatment holiday and control groups who meet the protocol-defined withdrawal criteria specified in Section 4.4 at any time during Year 1 or the additional years will undergo assessments scheduled at the Exit visit (Week 52) in Table 2 except for dosing with belimumab. At approximately 16 weeks after the withdrawal visit or the last dose of belimumab as appropriate, these subjects will also undergo the assessments scheduled at the 16-week follow-up visit; the 6 month follow-up visit is scheduled only for these discontinued subjects in the treatment holiday or control groups who have an anti-belimumab antibody response at the 16-week follow-up visit (or the last immunogenicity assessment if the 16-week follow-up is not available).

To:

Subjects in the treatment holiday and control groups who meet the protocol-defined withdrawal criteria specified in Section 4.4 at any time during Year 1 or the additional years will undergo assessments scheduled at the Exit visit (Week 52) in Table 2 except for dosing with belimumab. At approximately 16 weeks after the withdrawal visit or the last dose of belimumab as appropriate, these subjects will also undergo the assessments scheduled at the 16-week follow-up visit; the 6 month follow-up visit is scheduled only for these discontinued subjects in the treatment holiday or control groups.

Rationale: Provides clarification of protocol wording. The sentence should have been truncated prior to protocol amendment 5 publishing.

Change 12: Section 6.1.4 Definitions of SLE Flares Used in This Study

Change from:

2. A reproducible increase in serum creatinine of >20% or at least 0.3 mg/dL, accompanied by proteinuria (>1 g/24 hour equivalent), haematuria (\geq 4 red blood cells [RBCs]/high-power field [hpf]), and/or RBC casts.

3. Treatment emergent, reproducible haematuria (\geq 11 to 20 RBCs/ hpf) or a reproducible increase in haematuria by 2 grades compared with baseline, associated with >25% dysmorphic RBCs, glomerular in origin, exclusive of menses, accompanied by either an

0.8 g increase in 24-hour urinary protein levels (equivalent) or new-RBC casts [Alarcón-Segovia, 2003].

To:

2. A reproducible increase in **GFR** of >20% accompanied by **at least one of the following:** proteinuria (>1 g/24 hour equivalent), **and/or cellular** (RBC **or WBC**) casts [Alarcón-Segovia, 2003].

Rationale: Remove hematuria criteria from definition of renal flare.

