2.1. Changes to the Protocol Defined Statistical Analysis Plan

Changes from the originally planned statistical analysis specified in the protocol are outlined in Table 2.

	otocol	Reporting & Analysis Plan		
Statistical Analysis Plan		Statistical Analysis Plan	Rationale for Changes	
•	Partial prothrombin time (PTT) is collected	 Activated partial prothrombin time (aPTT) time is analyzed 	aPTT was collected instead of PTT	
•	Section 8.1.3 states that for the primary analysis of the additional efficacy and biomarkers, the baseline will be defined as study Day 0 of the original parent study. Additionally, for some of the endpoints, a secondary analysis will be performed by defining the baseline as Day 0 of the BEL116027 study.	• The baseline for each endpoint is defined per Section 6.1 of the protocol.	The protocol was inconsistent in the definition of baseline. See RAP Section 5.3 for clarification	
•	Immunogenicity is listed as a secondary endpoint in Protocol Section 6.1.2., but as an exploratory laboratory parameter in the Time and Events table.	 Immunogenicity is defined as a secondary endpoint. 	 The protocol was inconsistent, so the correct category was used in the RAP. 	
•	Renal flares are not listed as an endpoint in Protocol Section 6.1.2 nor described in Protocol Section 8, but are defined in Protocol Section 6.1.4	 Renal flares are included as an exploratory endpoint in RAP Section 2.2. 	 The protocol was inconsistent, so the endpoint was correctly specified in the RAP. 	
•	The definition of renal flare contained a typographical error and referenced an increase rather than a decrease in GFR. This was corrected in a note to file.	 The RAP specifies the correct definition, referencing a decrease in GFR. 	The protocol was incorrect.	
•	Protocol Section 6.1.3 lists percent change in PGA.	 The RAP specifies change from baseline in PGA instead. 	Change from baseline is more clinically relevant and interpretable, particularly in the case of low baseline scores.	
•	Protocol Section 6.1.2 lists one time interval for percent change in B-cell subsets from Week 24, i.e., Week 24 to 52.	 In addition to this, the RAP specifies percent change from Week 24 to 32 and Week 24 to 40. 	The additional time intervals facilitate interpretation of the changes following the treatment holiday phase.	

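### The SAP's renal-flare table lists dysmorphic red cells where the protocol requires RBC casts, without declaring it, so the GFR arm misses a flare whose only accompanying finding is RBC casts

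*SAP*

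**What the plan says.** Protocol 6.1.4 defines a renal flare by either of two criteria, present at two or more consecutive visits. The first is a rise in proteinuria. The second is a GFR change of more than 20% with at least one accompanying finding: proteinuria above 1 g/24 h equivalent, "and/or cellular (RBC or WBC) casts".

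SAP 13.6.3 restates the second criterion as "A reproducible decrease in GFR of >20%, accompanied by proteinuria (>1), and/or cellular (RBC and WBC) casts". It then says: "The following table identifies the lab parameters to be used to evaluate the criteria in the renal flare definition above". Under the cellular-casts heading that table has two rows:

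- WBC cellular casts, `WBCSTM_URQ`
- dysmorphic RBCs, `DRBCM_URQ`

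There is no row for RBC casts.

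SAP Table 2 (section 2.1) lists departures from the protocol. Its only entry on the content of the renal-flare definition is the direction of the GFR change: "The RAP specifies the correct definition, referencing a decrease in GFR". Neither the dysmorphic-RBC row nor the changed conjunction is mentioned.

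**The concern.** The parameter table is what a programmer will implement. It puts one microscopy finding, dysmorphic red cells, in the place of another, red-cell casts. The sentence above it also joins the two cast types with *and* where the protocol has *or*. Followed as written, the derivation can give a different renal-flare status from the protocol definition. Two programmers could also derive different events from the same page.

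Time to first renal flare is exploratory, but Table 2.4 is marked for the headline package. Table 2.5 repeats it in subjects with baseline proteinuria above 0.5 g/24 h equivalent. A reader of either table would assume that the protocol definition applies, apart from the declared GFR correction.

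**Working it through.** **Are the two findings separate laboratory items?** Yes. The microscopy list in Protocol Appendix 5 runs together in the extracted text as "Dysmorphic RBC Casts (specified by type e.g., RBC, WBC". The types given, RBC and WBC, describe casts and would make no sense as types of dysmorphic red cell. The SAP's laboratory list (13.8.1) has the same entries, and SAP 13.6.3 itself treats dysmorphic RBCs as a parameter of its own. So casts are recorded by type, and dysmorphic RBCs are a different entry.

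**Logical comparison.** The plan gives no figure to reproduce, so I compare the rules directly. Take a reproducible GFR fall above 20% as given, and let P = uPCR above 1, R = RBC casts, W = WBC casts, D = dysmorphic RBCs.

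- Protocol: P or R or W
- SAP table, rows as alternatives: P or W or D
- SAP table, conjunction taken literally: P or (W and D)

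There are 2⁴ = 16 patterns. In the 8 with P present, all three rules count a flare. The other 8 are:

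| R | W | D | Protocol | SAP, *or* | SAP, *and* |
|---|---|---|---|---|---|
| no | no | no | no | no | no |
| no | no | yes | no | **yes** | no |
| no | yes | no | yes | yes | **no** |
| no | yes | yes | yes | yes | yes |
| yes | no | no | yes | **no** | **no** |
| yes | no | yes | yes | yes | **no** |
| yes | yes | no | yes | yes | **no** |
| yes | yes | yes | yes | yes | yes |

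- *Or* reading: 1 of 16 patterns missed (RBC casts only), 1 of 16 wrongly counted (dysmorphic RBCs only).
- *And* reading: 4 of 16 missed, including RBC casts only and WBC casts only; none wrongly counted.
- SAP sentence alone, with true RBC casts and a literal *and*, P or (R and W): 4 of 16 missed, again including RBC casts only; none wrongly counted.
- After the fix below, P or R or W: 0 missed, 0 wrongly counted.

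These are counts of logical patterns, not event rates.

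**Weight of one subject.** Enrolment is 12, 29 and 39 (SAP 2.3). One reclassified subject moves the crude proportion with a renal flare by:

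- treatment holiday: 1/12 = 8.3 points
- control: 1/29 = 3.4 points
- long-term discontinuation: 1/39 = 2.6 points

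**The case against.** Several points narrow the matter, and most of them stand.

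- **Scope.** The endpoint is exploratory and all results are descriptive. Only the GFR arm is touched, only when uPCR is not above 1, and only when the pattern recurs at consecutive visits. Entry to the holiday and control groups requires a SELENA SLEDAI score of 3 or less, and each renal item scores 4, so those subjects enter without scored renal activity. All of this stands.
- **Casts are scored elsewhere.** Urinary casts are a 4-point SELENA SLEDAI item assessed at every Year 1 visit, and SAP 13.6.3 checks programmatically for a rise of at least 3 as a mild/moderate SFI flare. New casts with no offsetting improvement would therefore still register in the primary endpoint. This stands, but it does not repair the renal-flare tables.
- **The conjunction may be harmless.** The parenthesis may simply list the cast types, since the table gives each parameter its own row and states no joint requirement. That is a fair reading. It leaves the wording ambiguous and does not supply the missing RBC-cast row.

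Two stronger inferences are tempting, and the documents do not support either.

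- A reader might infer that the SAP counts a criterion deleted by Amendment 06, whose stated reason was "Remove hematuria criteria from definition of renal flare". The deleted criterion required reproducible haematuria, "associated with >25% dysmorphic RBCs, glomerular in origin, exclusive of menses", plus either a 0.8 g protein increase or new RBC casts, and it had no GFR component. The SAP reuses one qualifier from it, in a different role and without the 25% threshold. The haematuria criterion is not reinstated.
- A reader might infer that the SAP both misses events through *and* and adds events through dysmorphic RBCs. Those effects need opposite readings. Extra events arise only under *or*. Under a literal *and*, dysmorphic RBCs count only alongside WBC casts, which already qualify under the protocol.

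**Conclusion.** The mismatch is real, and the rule is wrong as written rather than merely short of detail. The SAP table cannot implement the protocol's cast criterion, because it never reads RBC casts. A protocol-defined flare whose only accompanying finding is RBC casts is missed under every reading. Whether subjects with dysmorphic RBCs only are added, or subjects with WBC casts only are also lost, depends on how the wording is taken.

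The practical size is unknown, because the documents give no frequency for any of these patterns. The per-subject percentages show how much one case would weigh in groups this small; they do not estimate how many cases there will be. The conclusion rests on dysmorphic RBCs and RBC casts being distinct recorded items, which the laboratory lists support, and on the parameter table being operative, which the SAP states. It is worth correcting because the result goes into a headline display under an undeclared change of definition. It does not bear on the primary analysis.

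**What to change.** In SAP 13.6.3:

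1. Reword the GFR criterion so that any single finding suffices, for example: *accompanied by at least one of proteinuria (>1) or cellular casts (RBC or WBC)*.
2. Replace the `DRBCM_URQ` row with the RBC-cast parameter from the urinalysis microscopy data, and keep `WBCSTM_URQ`. No RBC-cast test code appears in the documents, so it must be confirmed in the SI dataset first.
3. If RBC-cast data prove unavailable, keep dysmorphic RBCs only as a declared substitute: enter it in SAP Table 2 with a justification and state what counts as positive, since the parameter table gives no threshold.

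The cost is one sentence, one table row and a check of the dataset codes, plus a Table 2 entry if the substitute is kept. No new data collection is needed if casts were recorded by type as the laboratory lists show.

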Additional eligibility criteria for subject enrolment in the **long-term discontinuation group** in the study:

- 1. **Continuation studies:** Voluntarily withdrawn from continuation studies BEL114333, HGS1006-C1066, or LBSL99 and have withdrawn from belimumab therapy for no longer than 8 weeks prior to entry into this study.
- **Note:** investigators may stop, start, and/or change SLE medications and dosages as deemed necessary; yet long-term discontinuation subjects will remain on local standard of care SLE treatment therapy as determined by the physician during the study, or will need to be withdrawn.

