5.5.1. Permitted Medications and Non-Drug Therapies

Subjects in the treatment holiday and control groups must be on a stable SLE treatment regimen during the 30 day screening period prior to Day 0.

After Day 0, the investigator may adjust concurrent medications (add, eliminate, change dose level/frequency) as clinically required in response to improving or worsening conditions for the treatment holiday and control groups.

Note: Live vaccines are permitted for subjects in the long-term discontinuation group. Subjects in the control and treatment holiday groups are prohibited from receiving live vaccines.

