5.5.2. Prohibited Medications and Non-Drug Therapies

Subjects in the **treatment holiday and control groups** who start prohibited medications or therapies at any time during the study must be withdrawn from the study. These subjects will return for the EXIT visit, and the follow-up visits 16 weeks and 6 months after receiving their last dose of belimumab as described in Section 4.4.

The following medications and therapies are prohibited at any time during the study:

- Other investigational agents (biologic or non-biologic). Investigational applies to any drug not approved for sale in the country in which it is being used.
- Co-enrolment into another study of an investigational agent or non-drug therapy that may interfere with the conduct of this protocol.
- Anti-TNF or anti-IL-6 therapy (e.g., adalimumab, etanercept, infliximab, tocilizumab).
- Other biologics (e.g., rituximab, abatacept, interleukin-1 receptor antagonist [anakinra]).

- Intravenous immunoglobulin (IVIG).
- IV cyclophosphamide.
- Plasmapheresis, leukapheresis.

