7.2.4.3. Changes in Corticosteroid Use

7.2.4.3.1. Number of days of daily prednisone dose ≥7.5 mg/day and/or increased by 25%

The Dropout (DO)/Prohibited Medication (PM)=Non-responder (NR) imputation will be applied. If a subject withdraws from the study and/or receives a protocol-prohibited medication, the subject will be considered to have met this endpoint criteria (i.e, dose \geq 7.5 mg/day and/or increased by 25%) after the date of dropout or the date that the medication is started, whichever comes first, up until the visit date, and for those days in intervals for subsequent attended visits. Before this date, the evaluated endpoint will be assessed using available data.

7.2.4.3.2. Number of days of daily prednisone dose ≤7.5 mg/day and/or decreased by 25%

The Dropout (DO)/Prohibited Medication (PM)=Non-responder (NR) imputation will be applied. If a subject withdraws from the study and/or receives a protocol-prohibited medication, the subject will be considered a non-responder for this endpoint criteria (i.e., dose >7.5 mg/day and/or did not decreased by 25%) after the date of dropout or the date that the medication is started, whichever comes first, and for those days in intervals for subsequent attended visits. Before this date, the evaluated endpoint will be assessed using available data.

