13.7.2.1. Handling of Missing and Partial Dates

Element	Reporting Detail				
General	Partial dates will be displayed as captured in subject listing displays.				
Adverse Events	 The eCRF allows for the possibility of partial dates (i.e., only month and year) to be recorded for AE start and end dates; that is, the day of the month may be missing. In such a case, the following conventions will be applied for calculating the time to onset and the duration of the event: Missing Start Day: First of the month will be used unless this is before the start date of study treatment; in this case the Day 0 visit date (LTD and TH arms) or the study treatment start date (TC arm) will be used and hence the event is considered On-treatment as per Appendix 4: Study Phases and Treatment Emergent Adverse Events. Missing Stop Day: Last day of the month will be used, unless this is after the stop date of study treatment; in this case the study treatment stop date will be used. 				
	• Completely missing start or end dates will remain missing, with no imputation applied. Consequently, time to onset and duration of such events will be missing.				
Concomitant Medications and Medical History	• Medications with partial or missing start and/or stop dates will be assumed to be concomitant unless there is evidence through comparison of partial dates to suggest otherwise, for example if the day is missing, then the month and year will be compared to the month and year of the first dose date of study treatment and if the month and year are the same or later, then the medication will be considered concomitant.				

Element	Reporting Detail
Time to SFI	Evaluated up to Week 52
Flares	 If a subject takes a prohibited medication during the time period being analyzed, the subject will be considered as having a SFI flare at the start date of the prohibited medication.
	 If a subject withdraws from the study, the will be censored at last flare assessment date
	 If a subject dies, censor at the date of death
Time to Renal	Evaluated up to Week 52
Flare	• If a subject withdraws from the study, the will be censored at last renal flare assessment date
	If a subject dies, censor at the date of death
Number of SFI Flares	• If a subject withdraws from the study, dies or takes a prohibited medication, the subject will be considered as having a SFI flare.

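### SAP 13.6.3 ties intra-articular steroids to the prohibited-medication rules, against protocol 5.5.2 and the SAP's own coding, so a joint injection could be counted as a flare event

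*SAP*

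**What the plan says.** SAP 13.6.3, under Prednisone Equivalent Conversion, lists the routes by which a concomitant medication is identified as a steroid. After the systemic routes it adds "Although not systemic, intra-articular steroids are also identified for", and the sentence ends with "prohibited medication rules". Two later bullets in the same section call for reviews at database release that again cover systemic and intra-articular routes together.

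Protocol 5.5.2 opens its list with "The following medications and therapies are prohibited at any time during the study". Seven entries follow: investigational agents, co-enrolment in another study, anti-TNF or anti-IL-6 therapy, other biologics, IVIG, IV cyclophosphamide, and plasmapheresis or leukapheresis. For the treatment holiday and control groups, protocol 5.5.1 says that after Day 0 "the investigator may adjust concurrent medications (add, eliminate, change dose level/frequency) as clinically required". For the long-term discontinuation group, the note in protocol 4.2 says "investigators may stop, start, and/or change SLE medications and dosages as deemed necessary".

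Protocol 8.1.2 and SAP 7.1.4 count a prohibited medication as a flare event. The handling table in SAP Appendix 7 repeats the rule: "the subject will be considered as having a SFI flare at the start date of the prohibited medication".

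**The concern.** A medication class that the protocol leaves open is linked, in one SAP sentence, to rules that create endpoint events. If the link is programmed, a subject who has a joint injection and no SFI flare enters the primary analysis as having flared on the injection date.

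The same treatment of prohibited medication appears in SAP 7.2.4.1 (flare rate and first severe flare) and 7.3.4.3 (renal flare), so the injection could also be reported as a severe or renal flare. Tables 2.1, 2.3 and 2.4, which carry time to first SFI flare, first severe flare and first renal flare, are all marked as headline results. The groups are small and the study reports descriptive estimates only, so correct classification of single events carries much of the weight.

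**Working it through.** The plan states no figure on this point, so there is nothing to reproduce. The check is a comparison of texts, followed by arithmetic for scale.

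**Is an intra-articular steroid prohibited?**
- Protocol 5.5.2: no. None of the seven entries is a steroid.
- Protocol 5.5.1: no. Its only prohibition is on live vaccines in the holiday and control groups.
- Protocol 4.3: no. The prednisone limit there is an eligibility rule for the screening period.
- SAP 2.1: the table of changes from the protocol declares no widening of the prohibited list.
- SAP 13.6.2: no. The PROHIBITED category names specific drugs plus plasmapheresis. An injected steroid would be coded to the steroid category by its ATC code. It would then get SYSTEMIC = N, because intra-articular is not among the systemic routes, and that section evaluates only medication with systemic exposure.
- SAP 13.6.3: implied yes, through its stated purpose.

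**Which text governs?** The SAP does not say. Section 13.6.2 does not settle it, for two reasons. Its table concerns allowable SLE medication at baseline, not events on study. It is also not a full copy of protocol 5.5.2: tocilizumab, IV cyclophosphamide and leukapheresis are missing from the PROHIBITED row, and cyclophosphamide is coded as an immunosuppressant.

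**Which endpoints could be reached?**
- SAP 7.1.4, 7.2.4.1 and 7.3.4.3 refer to a prohibited medication without saying whose list defines it. Time to first SFI flare, first severe flare, flare rate and renal flare are therefore exposed.
- SAP 7.2.4.3 is worded differently: "If a subject withdraws from the study and/or receives a protocol-prohibited medication, the subject will be considered to have met this endpoint criteria". It is limited to medication that the protocol prohibits, so the prednisone-day endpoints are not exposed as written.

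**Scale.** Enrolled numbers from SAP 2.3 are 12 (treatment holiday), 29 (control) and 39 (long-term discontinuation). One reclassified subject moves the crude flare proportion by 100/n points:
- Treatment holiday: 100/12 = 8.3
- Control: 100/29 = 3.4
- Long-term discontinuation: 100/39 = 2.6

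These are upper limits per affected subject. They apply only if the subject has no true SFI flare in the 52 weeks. If a true flare comes after the injection, the event date moves earlier and the proportion does not change. If it came before, time to first flare does not change, although the flare count could still gain an event.

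**How likely is one affected subject?** The documents give no injection rate. As an assumption, let each subject have probability p of an injection over 52 weeks, with p between 1% and 10%. The chance of at least one in a group is 1 − (1 − p)^n:
- Treatment holiday: 1 − 0.99^12 = 0.11 to 1 − 0.90^12 = 0.72
- Control: 1 − 0.99^29 = 0.25 to 1 − 0.90^29 = 0.95
- Long-term discontinuation: 1 − 0.99^39 = 0.32 to 1 − 0.90^39 = 0.98

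The range is wide because p is unknown. It shows only that the case cannot be dismissed as impossible.

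**The case against.** The best defence is that SAP 13.6.3 only identifies a route and never says that joint injections are prohibited. With no steroid entry in protocol 5.5.2, the clause may have nothing to act on. The only executable definition, in 13.6.2, would exclude an injection on both the drug list and the route. On this view the clause is a stray line with no effect. It stands to this extent: a reader might infer that the SAP requires every joint injection to be counted as a flare, and the documents do not support that. They contradict each other without mandating the error. The defence does not remove the problem, because the clause names its purpose, two further bullets in 13.6.3 carry the intra-articular route forward, and 13.6.2 is neither complete nor written for on-study events.

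A second defence is that many affected subjects would flare anyway. SAP section 2 gives pooled BLISS flare percentages of 57.5% to 74.6% on 10 mg/kg and 68.5% to 81.5% on placebo. Signs and symptoms and new medication for disease activity are also SFI components (protocol 6.3.1.3), so an injection for lupus arthritis may coincide with a true flare. This is fair, and it is why the percentage-point figures are ceilings. The BLISS figures are only indicative for the subjects enrolled here.

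A misapplied flag would also be visible, since Listing 10 shows every subject recorded as taking prohibited medication.

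**Conclusion.** The inconsistency is real and should be resolved before the flare analyses are run. As the SAP stands, an injection that the protocol does not prohibit could be counted as an event in four flare analyses, including the primary one. The effect is at most 8.3, 3.4 or 2.6 points on a group's crude flare proportion for each affected subject with no true SFI flare. It rests on the 13.6.3 clause being programmed and on at least one such injection occurring, for which the documents give no rate. The study is descriptive with no power calculation, so event counts, event dates and product-limit estimates are at stake, and no error rate or power is.

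A reader might also infer that an injection fills the raised-prednisone endpoint for the rest of follow-up. That does not follow: SAP 7.2.4.3 and the matching entries in Appendix 7 apply only to protocol-prohibited medication, which this is not.

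**What to change.** Reconcile SAP 13.6.3 with protocol 5.5.2 and SAP 13.6.2:
- Delete the intra-articular clause in 13.6.3.
- Align the two later bullets in 13.6.3, on conversion factors and on routes, which also name the intra-articular route.
- State in 7.1.4, 7.2.4.1, 7.3.4.3 and Appendix 7 that the flare-event rules use only the protocol 5.5.2 list.
- Check the programmed prohibited-medication flag against that list.

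If the sponsor intends the wider rule, declare and justify it in SAP 2.1 as a departure from the protocol and add it to the coded list in 13.6.2.

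The cost is a few lines of SAP text and one programming check. No data collection changes. The point concerns how events are classified in the analysis, not how subjects are treated.
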